17.3 Sample Size

This phase I study is expected to require 9 evaluable patients to establish the highest dose level as the MTD. We do not expect serious adverse events or DLTs based on experience of treating patients with Y90-RE. Experience with immunotherapy as well has been reassuring from a safety perspective. Anecdotally, we have had some patients who were on immunotherapy for HCC, which got FDA approved in October 2017 who got Y90-RE with no untoward side effects and good responses. Given the clinical experience and data that is available so far, we do not expect to reach the maximum accrual dictated by budget restrictions during the MTD determination portion of the study. Once the MTD is determined, additional patients will be accrued in an expansion cohort in order to reach full accrual of 18 patients between Phase I and the expansion cohort.

The primary objective of the expansion cohort is to evaluate whether Y90-RE in combination with durvalumab confers an immune response (mechanism of action) irrespective of dose level as estimated by the change in frequency of immune cells pre- and post-treatment. A sample size of 18 patients will allow the sample mean for the pairwise difference to be estimated with a 95% confidence interval half-width of 0.5 SD.

The overarching goal of the expansion cohort is to gain preliminary evidence as to whether Y90-RE in combination with durvalumab confers an immune response, the hypothesized mechanism of action. Immune response will be assessed by estimating the mean change in the frequencies of immune cells from pre-treatment to post-treatment. More specifically, each patient's immune cell frequencies at pre-treatment will be subtracted from the post-treatment value to obtain the pairwise difference for a patient. Immune cell analysis will include, but is not limited to, the frequencies of innate (monocytes, macrophages, neutrophils, dendritic cells, NK cells) and adaptive (CD4+ T cells, CD8+ T cells, NKT cells, B cells) immune cells. A change in immune cell frequencies after treatment is anticipated, but the expected average change for each type of immune cell is not known, thus the purpose of the expansion cohort. No formal hypotheses are being tested, rather the change in immune profile along with other data obtained (e.g. changes in circulating tumor DNA, tumor response to treatment, etc.) will be collectively evaluated and used to inform a subsequent Phase II trial. From previously done similar studies, a 25% change is taken to represent a biologically meaningful downregulation of some of the key negative players (e.g. Tregs) and upregulation of positive players (e.g. PD-L1) expression, which will be taken into consideration when evaluating the immune profile.

17.4 Accrual and Study Duration

Given previous data for the similar studies and our clinical volume, it is expected that the annual accrual rate will be **12** patients. With that being said, we expect full accrual to be reached within **18** months if not sooner.

17.5 Analysis Plans

All the relevant results pertaining to toxicity, MTD, response, timed endpoints and laboratory correlates will be examined in an exploratory and hypothesis-generating fashion. The small sample size and the heterogeneous patient population associated with phase I studies restricts the generalizability of the results. Any notable statistical result should only be viewed as an impetus for further study in Phase II trials rather than a definitive finding in and of itself.

17.5.1 Adverse Events Profile

The number and severity of all adverse events (overall, by dose-level, and by tumor group) will be tabulated and summarized in this patient population. The Grade 3+ adverse events will also be described and summarized in a similar fashion. This will provide an indication of the level of tolerance for this treatment combination in this patient group.

17.5.2 Toxicity Profile

The term toxicity is defined as adverse events that are classified as either possibly, probably, or definitely related to study treatment. Non-hematologic toxicities will be evaluated via the ordinal CTC standard toxicity grading. Hematologic toxicity measures of thrombocytopenia, neutropenia, and leukopenia will be assessed using continuous variables as the outcome measures (primarily nadir) as well as categorization via CTC standard toxicity grading.

Overall toxicity incidence as well as toxicity profiles by dose level, patient and tumor site will be explored and summarized. Frequency distributions, graphical techniques and other descriptive measures will form the basis of these analyses.

Please note for the response/efficacy evaluation, it will be mRECIST as well as iRECIST that will be reported. A confirmatory scan can be done 4 weeks post completion of therapy if there are clinical concerns.

17.5.3 Overall Response Rate

Overall response rate is defined as the proportion of evaluable patients that have achieved a complete response or partial response using mRECIST evaluation criteria. ORR will be evaluated at 2 months post-Y90RE treatment (\pm 5 business days).

ORR will be analyzed descriptively as a point estimate with a 95% confidence interval.

Results will be reported consistent with RECIST v1.1 (Appendix A.9).

An “evaluable subject” for the purpose of evaluation of the combinatorial therapy is one who receives both Y90-radioembolization and at least 1 dose of durvalumab.

Subjects who do not receive Y90-RE or received only a single incomplete dose of immunotherapy (i.e., allergic reaction), are considered non-evaluable for assessment of efficacy. These subjects would be replaced for the proposed sample size of 18.

All subjects included in the study must be assessed for response to treatment, even if there are major protocol treatment deviations or if they are ineligible.

Each subject will be assigned one of the following categories: 1) complete response (mRECIST), 2) partial response (mRECIST), 3) stable disease (mRECIST), 4) progressive disease (mRECIST), 5) early death from malignant disease, 6) early death from toxicity, 7) early death because of other cause, or 9) unknown (not assessable, insufficient data).

Category 4 (protocol specific definition): includes clinical progression as determined by the principal investigator and confirmed by the independent data and safety monitoring committee (DSMC).

Category 5 (protocol specific definition): death from malignant disease as determined by the principal investigator and confirmed by the independent data and safety monitoring committee (DSMC).

Category 6 (protocol specific definition): death from toxicity as determined by the principal investigator and confirmed by the independent data and safety monitoring committee (DSMC).

Category 7 (protocol specific definition): includes death not meeting categories 5 or 6, or death defined as not otherwise specified.

Category 9 (protocol specific definition): includes subjects who did not receive radioembolization, or who did not receive at least 1 complete infusion of durvalumab, or who did not undergo follow-up imaging (other than for clinical progression, toxicity, or death), or subjects who are lost to follow-up.

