13.9 Ineligible

A patient is deemed *ineligible* if after enrollment, it is determined that at the time of screening, the patient did not satisfy each and every eligibility criterion for study entry. If the patient received treatment, the patient may continue treatment at the discretion of the physician as long as there are not safety concerns. The patient will continue in the Active Monitoring/Treatment phase of the study, as per section 4.0 of the protocol.

If the patient never received treatment, on-study material must be submitted. Survival Follow-up will be required per Section 4.0 of the protocol.

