- SD is measured from the start of the treatment until the criteria for disease progression are met, taking as reference the smallest measurements recorded since the treatment started.
- The clinical relevance of the duration of SD varies for different tumor types and grades. Therefore, it is highly recommended that the protocol specify the minimal time interval required between two measurements for determination of SD. This time interval should take into account the expected clinical benefit that such a status may bring to the population under study.

A.8 Response review

- For trials where the response rate is the primary endpoint it is strongly recommended that all responses be reviewed by an expert(s) independent of the study at the study's completion. Simultaneous review of the patients' files and radiological images is the best approach.

A.9 Reporting of results

- All patients included in the study must be assessed for response to treatment, even if there are major protocol treatment deviations or if they are ineligible. Each patient will be assigned one of the following categories: 1) complete response, 2) partial response, 3) stable disease, 4) progressive disease, 5) early death from malignant disease, 6) early death from toxicity, 7) early death because of other cause, or 9) unknown (not assessable, insufficient data).
- All of the patients who met the eligibility criteria should be included in the main analysis of the response rate. Patients in response categories 4-9 should be considered as failing to respond to treatment (disease progression). Thus, an incorrect treatment schedule or drug administration does not result in exclusion from the analysis of the response rate. Precise definitions for categories 4-9 will be protocol specific.
- All conclusions should be based on all eligible patients.
- Subanalyses may then be performed on the basis of a subset of patients, excluding those for whom major protocol deviations have been identified (e.g., early death due to other reasons, early discontinuation of treatment, major protocol violations, etc.). However, these subanalyses may not serve as the basis for drawing conclusions concerning treatment efficacy, and the reasons for excluding patients from the analysis should be clearly reported.
- The 95% confidence intervals should be provided.

IV.B. Immunotherapy in cancer Response Evaluation Criteria in Solid Tumors (iRECIST) Quick Reference

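### Section 17.5.3 drops and replaces eligible patients whom the A.9 rule it cites counts as response failures, and 17.5.5 times survival from a randomization that this single-arm trial does not have

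*Combined protocol and SAP*

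**What the plan says.** Section 17.5.3 defines ORR as a proportion of evaluable patients, meaning those who received Y90-RE and at least one dose of durvalumab. Patients who had no Y90-RE, or who "received only a single incomplete dose of immunotherapy (i.e., allergic reaction), are considered non-evaluable for assessment of efficacy", are replaced: "These subjects would be replaced for the proposed sample size of 18". The section also states: "Results will be reported consistent with RECIST v1.1 (Appendix A.9"). It requires every subject to be assessed and given a response category, and its category 9 "includes subjects who did not receive radioembolization", along with those who had no complete durvalumab infusion.

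Appendix IV.A, A.9 states: "All of the patients who met the eligibility criteria should be included in the main analysis of the response rate". It continues: "Patients in response categories 4-9 should be considered as failing to respond to treatment (disease progression"). Analyses that exclude patients for protocol deviations are allowed, but "these subanalyses may not serve as the basis for drawing conclusions concerning treatment efficacy".

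Section 17.5.4 defines the disease control rate (DCR) on evaluable patients too. Section 13.8 has a different replacement trigger: first cycle not completed, before Y-90, for reasons other than toxicity. Section 13.9 covers patients found ineligible once enrolled, that is, when "it is determined that at the time of screening, the patient did not satisfy each and every eligibility criterion for study entry"; such a patient, if already treated, may continue.

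For overall survival (OS), 17.5.5 starts the clock at randomization. Section 17.1 describes a single-arm study, and the footnote to 2.2 sets the start of immunotherapy as the landmark in all instances.

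**The concern.** Section 17.5.3 takes over A.9's category list and commits to its reporting rule, but uses a denominator that A.9 does not allow for the main analysis. An eligible patient who never receives Y90-RE is outside the ORR under one sentence and a failure inside it under another. Two analysts following the section could report different rates from the same patients.

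The protocol's own rules can produce such patients. At levels 1 to 4, Y90-RE comes two weeks after the first durvalumab dose (7.1.2). In that gap, Table 8.21 ends all protocol treatment after a grade 3 or 4 infusion reaction, and 13.2 moves a patient who progresses on therapy to survival follow-up. An early failure can therefore leave the denominator and be replaced by someone who got further.

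ORR is a secondary goal, 17.5 calls all results exploratory, and no threshold depends on it. However, 17.3 lists tumor response among the data that will inform a Phase II trial.

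The OS definition cannot be carried out as written, because the date it names does not exist.

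**Working it through.** **The plan's own figures.** The documents give no precision figure for ORR, DCR or OS. The one figure tied to N = 18 (17.3) is a 95% half-width of 0.5 SD for a mean paired immune-cell difference. It reproduces: t(0.975, 17)/√18 = 2.110/4.243 = 0.497. It does not bear on the ORR denominator.

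**The two rules side by side.**

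| Patient | 17.5.3 ORR | A.9 main analysis |
|---|---|---|
| Eligible, no Y90-RE or only one incomplete durvalumab dose | Left out, replaced | In, failure |
| Eligible, both treatments, no imaging or lost to follow-up | In, not a responder | In, failure |
| Both treatments, later found ineligible (13.9) | In | Out |

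The first row holds whatever category the patient gets. Progression or death before Y90-RE may be coded 4 to 7 instead of 9, but A.9 counts all of 4 to 9 as failures.

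**Formula.** Let x be the responders among the 18 evaluable patients, m the eligible patients dropped and replaced, k the evaluable patients later found ineligible, and r the responders among those k.

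- 17.5.3 rate = x/18
- A.9 rate = (x − r)/(18 + m − k)

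With r = 0, the 17.5.3 rate exceeds the A.9 rate by (m − k)/18 in relative terms. None of x, m, k or r is in the documents; m and k may both be 0. Intervals are exact (Clopper-Pearson) 95%; the plan does not name a method.

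**ORR with x = 6 assumed.**

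| Case | Rate | 95% CI | 17.5.3 rate relative to this |
|---|---|---|---|
| 17.5.3 | 6/18 = 33.3% | 13.3 to 59.0 | – |
| A.9, m = 1, k = 0 | 6/19 = 31.6% | 12.6 to 56.6 | 1/18 = 5.6% higher |
| A.9, m = 2, k = 0 | 6/20 = 30.0% | 11.9 to 54.3 | 2/18 = 11.1% higher |
| A.9, m = 0, k = 1, r = 0 | 6/17 = 35.3% | 14.2 to 61.7 | 1/18 = 5.6% lower |
| A.9, m = 0, k = 1, r = 1 | 5/17 = 29.4% | 10.3 to 56.0 | higher |
| A.9, m = 1, k = 1, r = 0 | 6/18 = 33.3% | 13.3 to 59.0 | equal |

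If every evaluable patient is eligible (k = 0), the 17.5.3 rate is never below the A.9 rate. If k is above 0, the difference can go either way.

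**DCR with 12 controlled assumed.** 12/18 = 66.7% (41.0 to 86.7) against 12/20 = 60.0% (36.1 to 80.9) at m = 2, k = 0.

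**How likely is m ≥ 1?** Assume independent loss with probability p per enrolled patient and enrollment until 18 are evaluable. Then the expected m is 18p/(1 − p), and P(m ≥ 1) = 1 − (1 − p)^18.

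| p (assumed) | Expected m | P(m ≥ 1) |
|---|---|---|
| 2% | 0.4 | 30% |
| 5% | 0.9 | 60% |
| 10% | 2.0 | 85% |

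Section 1.4.6 states a 10% loss for dose escalation only. Using it here assumes that it applies to all 18 and that every loss is an eligible patient dropped under 17.5.3, so it is an upper case.

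**OS origin.** No randomization takes place. At levels 1 to 4 durvalumab comes first, so first study treatment and the 2.2 landmark are the same date. At levels −1 and −2, which open only if the stopping boundaries are met, durvalumab follows Y90-RE, and the 2.2 landmark would start the clock after treatment had begun.

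**The case against.** The strongest reply is that the intended population is plain. Sections 17.5.3 and 17.5.4 define both rates on evaluable patients, and 1.4.7 points the same way. ORR is timed from Y90-RE, a date that a patient without Y90-RE does not have. A.9 is generic reference text, and 17.5.3 copies its category list but not its main-analysis sentence. On that reading, A.9 governs how categories are reported and the evaluable set governs the estimate. This does not fit the commitment in 17.5.3, which ties results to A.9 without qualification. Section 1.4.7 presumes that everyone received both treatments, so it does not address those who did not. The missing Y90-RE date is no obstacle under A.9, which counts such a patient as a failure without a scan.

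It can also be said that few early failures would be lost. No scan is scheduled between baseline and the end-of-treatment visit, so progression before Y90-RE would have to be clinical or found on unscheduled imaging, and infusion reactions are captured in the safety analyses. That stands as a limit on how often this happens. It does not settle the denominator for the patients concerned.

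The size is hypothetical and small, ORR is exploratory, and a treated-set analysis is a legitimate choice for a combination if it is stated. All of that stands and limits the weight of the point. The OS correction is minor, since the 2.2 footnote largely settles it.

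**Conclusion.** The concern holds. Section 17.5.3 gives two incompatible rules for an eligible patient who lacks Y90-RE or had only one incomplete durvalumab dose, and the documents do not say which controls. With 6 assumed responders and one or two such patients, ORR moves from 33.3% to 31.6% or 30.0%, well inside an interval of 13.3% to 59.0%. The direction is fixed only if all evaluable patients are eligible. No sample size, test or threshold changes. What is at stake is a single, reproducible definition of a secondary efficacy estimate that is meant to inform Phase II.

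The randomization origin in 17.5.5 is an error on its face, with little practical effect once corrected. The point should be addressed, preferably before response results are known.

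**What to change.** - **17.5.3:** make all eligible patients the main ORR denominator, with categories 4 to 9 as failures. The section already ties itself to A.9, and A.9 bars efficacy conclusions from subsets. Report the both-treatments set as supportive, with the number dropped and the reasons, and list treated patients later found ineligible separately.
- **17.5.4:** use the same denominator for DCR. This extends A.9, which names only the response rate, for consistency.
- **Replacement:** let replacements serve only the dose-finding and correlative counts, and state how 13.8 relates to 17.5.3. As a minor tidy-up, keep one of the two alternative wordings in 13.11, which differ on follow-up of patients removed before treatment.
- **17.5.5:** time OS from first study treatment, and align the 2.2 footnote for levels −1 and −2.

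If the sponsor prefers the treated set as the main analysis, the text should say so, remove the claim of consistency with A.9, and still report the all-eligible rate.

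The cost is wording in 17.5.3 to 17.5.5, 13.8, 13.11 and the 2.2 footnote. No new data are needed, because 17.5.3 already gives every subject a category. If all evaluable patients are eligible, the reported ORR and DCR will be equal or slightly less favorable; otherwise they may move either way.

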17.5.4 Disease Control Rate

Disease control rate is defined as the proportion of evaluable patients that have achieved a complete response, partial response, or stable disease by a specified time point. DCR will be evaluated at 2 months post-Y90RE treatment. DCR will be analyzed descriptively as a point estimate with a 95% confidence interval.

17.5.5 Overall Survival

Overall survival is defined as the time from randomization to death of any cause. Patients that are still alive at the time of analysis will be censored at the date they were last known to be alive. OS will be analyzed descriptively as a point estimate for the median with a 95% confidence interval using the Kaplan-Meier method.

17.5.6 Laboratory Correlates

Baseline tumor markers including CEA and CA-19-9 will be assessed and then at subsequent study visits. Complete differential would be obtained to assess and report neutrophil to lymphocyte ratio. Markers of inflammation ESR, CRP and vitamin D levels to be assessed at baseline and the subsequent visits.

17.6 Inclusion of Women and Minorities

This study will be available to all eligible patients regardless of race, gender, or ethnic group.

There is no information currently available regarding differential agent effects of either regimen in subsets defined by gender, race, or ethnicity, and there is no reason to expect such differences exist. Therefore, although the planned analyses will, as always, look for differences in treatment effect based on gender and racial groupings, the sample sizes are not increased in order to provide additional power for such subset analyses.

18.0 Pathology Considerations/Tissue Biospecimens

DNA and RNA extraction will be performed at University of Iowa. DNA and RNA sequencing will be performed at TEMPUS. The biopsies (both clinical and research) will be performed at University of Iowa. Detailed instructions in the companion laboratory manual.

Tissue Samples are held at the University of Iowa Tissue Procurement Core.

Contact:

[name]
Tissue Procurement Core
[name]
[name]
[name]

19.0 Records and Data Collection Procedures

19.1 Submission Timetable

Data submission instructions for this study can be found in the Data Submission Schedule.

19.2 Survival Follow-up

See [Section 4](#).

19.3 CRF completion

Data will be collected through HCCC's Clinical Trial Management System (OnCore). See Appendix V. A.

19.4 Site responsibilities

Each site will be responsible for insuring that all materials contain the patient's initials, registration number, and protocol number. Patient's name must be removed.

19.5 Supporting documentation

This study requires supporting documentation for diagnosis and progression prior to study entry as well as for evidence of response to study therapy and progression after study therapy. These documents should be submitted within 14 days of registration.

19.6 Labeling of materials

Each site will be responsible for insuring that all materials contain the patient's initials, registration number, and protocol number. Patient's name must be removed.

20.0 Budget

20.1 Costs charged to patient: routine clinical care

20.2 Tests to be research funded:

Research testing on blood and tissue specimens

20.3 Other budget concerns:

BTG International Canada, Inc. will provide University of Iowa with funding to support the costs of running this study.

AstraZeneca Pharmaceuticals will provide study drug durvalumab for use in this study

Appendix I: ECOG Performance Status**ECOG PERFORMANCE STATUS***

Grade	ECOG
0	Fully active, able to carry on all pre-disease performance without restriction
1	Restricted in physically strenuous activity but ambulatory and able to carry out work of a light or sedentary nature, e.g., light house work, office work
2	Ambulatory and capable of all selfcare but unable to carry out any work activities. Up and about more than 50% of waking hours
3	Capable of only limited selfcare, confined to bed or chair more than 50% of waking hours.
4	Completely disabled. Cannot carry on any selfcare. Totally confined to bed or chair.
5	Dead

*As published in Am. J. Clin. Oncol.:

The ECOG Performance Status is in the public domain therefore available for public use. To duplicate the scale, please cite the reference above and credit the Eastern Cooperative Oncology Group, Robert Comis M.D., Group Chair.

From http://www.ecog.org/general/perf_stat.html

